7.3.2.2. Best Overall Response

The BOR is the best response recorded from the start of the treatment until the first PD, in the order of CR, PR, SD, PD, and NE. Responses of CR, PR, or SD after a response of PD will not be considered in determining best response. The BOR will be determined from response assessments before or on the same day as new anticancer therapy. If any alternative cancer therapy is taken while on study, any subsequent assessments will be excluded from the BOR determination. In the case of SD, measurements must meet the SD criteria at least after the date of first dose at a minimum of 7 weeks.

7.3.3. Secondary Analysis

7.3.3.1. Duration of Response

Duration of response is defined as the time from first objective response (CR or PR) to the time of first documented PD or death due to any cause. If a participant does not have an event before data cutoff or new anticancer therapy, DOR is censored at the date of the last adequate tumor assessment before data cutoff or new anticancer therapy following the same algorithm as censoring of PFS (see Table 4). If there are sufficient observations for the responders, then a Kaplan-Meier estimate of the distribution function will be constructed for DOR, and the median

DOR along the 95% CI will be reported. If the number of observed responders in each treatment group is not sufficient to estimate median DOR, a swimmer plot and listing for DOR may be generated in place of the summary table.

Table 4: Evaluation and Censoring of Progression-Free Survival

Situation	Outcome	Date of Progression or Censoring
No baseline tumor assessments	Censored	Day 1
No valid postbaseline response assessments in the absence of death prior to first scheduled tumor assessment	Censored	Day 1
Progression documented between scheduled response assessments	Progressed	Date of first overall response of PD
No progression	Censored	Date of last valid radiologic assessment (not NE or missing)
Study withdrawal for undocumented progression	Censored	Date of last valid radiologic assessment (not NE or missing)
Study withdrawal for toxicity or other reason	Censored	Date of last valid radiologic assessment (not NE or missing)
New anticancer treatment started	Censored	Date of last valid radiologic assessment (not NE or missing) on/before starting a new anticancer treatment
Death before first progressive response assessment	Progressed	Date of death
Death between adequate response assessments	Progressed	Date of death
Death or documented progression immediately after missing 2 or more consecutive scheduled tumor assessment	Censored	Date of last valid radiologic assessment (not NE or missing) prior to missed assessments

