8.2. Efficacy Assessments

Objective assessment of disease status will be evaluated according to RECIST v1.1 (Eisenhauer et al 2009) and entered into the eCRF. Efficacy assessments of response should be performed according to schedule found in Table 3. Scans should follow calendar days and should not be delayed for treatment holds or interruptions. Confirmation of CR or PR should be confirmed by imaging at least 4 weeks after initial documentation.

Participants who discontinue study treatment will not require further disease assessments.

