10.4.2.3. Progression-Free Survival

Progression-free survival, defined as the time from first dose of study drug to the date of the first documented progression per RECIST v1.1 or death due to any cause. Progression free survival data will be analyzed by the Kaplan-Meier method, including estimated median with 95% CI, and Kaplan-Meier estimated probabilities at several timepoints. If an event is not observed, PFS will be censored at the last adequate tumor assessment before cutoff or new anticancer therapy.

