- Participants with a global deterioration of health status requiring discontinuation of treatment without objective evidence of disease progression at that time should be classified as having "symptomatic deterioration." Every effort should be made to document the objective progression even after discontinuation of treatment.
- In some circumstances, it may be difficult to distinguish residual disease from normal tissue. When the evaluation of CR depends on this determination, it is recommended that the residual lesion be investigated (fine needle aspirate/biopsy) to confirm the CR status.

Source: Eisenhauer et al 2009.

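### PFS and DOR are at risk of upward bias: progression without a RECIST record and new therapy are censored at the last scan, scans are not required after discontinuation, and no sensitivity analysis is planned

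*SAP*

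**What the plan says.** SAP Table 4 (section 7.3.3.1) sets the PFS censoring rules, and the text above it applies the same algorithm to DOR.

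- The row "Study withdrawal for undocumented progression" is censored at the last valid radiologic assessment.
- The row "New anticancer treatment started" is censored at the last valid scan on or before the new treatment.
- A participant who stops study drug but does not leave the study, and has no RECIST PD on record, falls under the no-progression row and is censored at the same point. Protocol 7.1.2 separates stopping drug from leaving the study.
- "Death before first progressive response assessment" is an event on the date of death.
- "Death or documented progression immediately after missing 2 or more consecutive scheduled tumor assessment" is censored at the last valid scan before the gap.

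Protocol 10.4.2.3 has the same general rule: "If an event is not observed, PFS will be censored at the last adequate tumor assessment before cutoff or new anticancer therapy".

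On imaging, Protocol 8.2 says: "Participants who discontinue study treatment will not require further disease assessments". The Schedule of Activities (Table 3) marks imaging at screening and every 8 weeks on treatment, but not at end of treatment or follow-up. Appendix B, on symptomatic deterioration, says: "Every effort should be made to document the objective progression even after discontinuation of treatment".

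SAP 7.3.3.1 and 7.3.3.3 describe one DOR and one PFS analysis. SAP Appendix A lists one summary table for each (2.2.1 and 2.2.2). No sensitivity analysis for either endpoint appears in the SAP or the Protocol.

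**The concern.** Kaplan-Meier estimation treats a censored participant as having the same future risk as those still under observation. Someone who stops for clinical decline, or is switched to another therapy, has often just failed or is about to. Censoring such people at their last good scan removes failures from the numerator and spreads the remaining risk over those who are doing better.

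Censoring undocumented progression is a common and defensible main rule when scans continue until objective PD, because most such participants then acquire a dated event. Where scans are not required after discontinuation, that correction is weakened.

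The study has a single arm per disease and no control group in which the bias could cancel. With no hypothesis test, the PFS and DOR estimates are themselves the result. As planned, a reader could not tell how far they depend on the censoring rule.

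**Working it through.** **The plan's own figures.** The documents give no PFS rate, event count or dropout rate. The only design figures are the exact 95% CIs for ORR with n = 30 (SAP Table 2, Protocol Table 13). All six rows reproduce by Clopper-Pearson limits (for example 9/30: 14.7 to 49.4). They do not bear on PFS.

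**Closed form.** Assume exponential failure with hazard λ, and let a share g of all failures be censored at the time of failure. Kaplan-Meier then estimates hazard (1 − g)λ, so the median is multiplied by 1/(1 − g): 1.05 at 5%, 1.11 at 10%, 1.25 at 20% and 1.43 at 30%.

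**Simulation.** 400,000 participants per scenario. Every input below is an assumption except the 8-week scan interval:

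- true median 6 months, exponential;
- scans every 8 weeks (1.84 months) throughout;
- follow-up uniform over 6 to 18 months;
- 10% of failures are deaths, always counted;
- a share f of the other failures is undocumented.

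Table 4 censoring is compared with counting the undocumented progression as an event on its date. Ranges cover three treatments of later deaths among the undocumented:

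1. never counted;
2. median 8 months from failure to death, half starting new therapy;
3. median 4 months to death, a quarter starting new therapy.

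In the second and third, a later death counts only if there was no new therapy and it fell within two scan intervals of the last scan. Gaps are taken within each variant.

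| f | 6-month PFS, Table 4 vs event | Gap (points) | 12-month PFS, Table 4 vs event | Gap (points) | Median (months), Table 4 vs event |
|---|---|---|---|---|---|
| 5% | 53.7–54.0% vs 52.5% | 1.2–1.5 | 28.5–29.0% vs 27.1–27.3% | 1.3–1.7 | 7.36 vs 7.36 |
| 10% | 54.6–55.4% vs 52.3% | 2.3–3.1 | 29.5–30.4% vs 26.9–27.0% | 2.5–3.4 | 7.36 vs 7.36 |
| 20% | 56.9–58.3% vs 51.9–52.1% | 4.9–6.4 | 31.7–33.6% vs 26.4–26.5% | 5.3–7.2 | 7.36 vs 7.21–7.33 |
| 30% | 59.1–61.7% vs 51.7% | 7.4–10.0 | 34.1–37.8% vs 26.0–26.1% | 8.0–11.7 | 7.36–9.20 vs 6.77–6.79 |

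**Cross-check.** With 10% deaths, the share of all failures censored is g = 0.9f. When later deaths are never counted, the closed form gives 6-month PFS of 0.5^(1 − 0.9f): 53.2%, 56.6% and 60.3% at f = 10%, 20% and 30%. Against the exponential 50%, the gaps are 3.2, 6.6 and 10.3 points, close to the top of the simulated ranges (3.1, 6.4 and 10.0).

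**Reading the table.** The comparison is between two rules, not with the truth. The true 6-month PFS here is 50%. The values near 52% arise because progression is dated at the next scan, so failures after the 5.52-month scan are mostly not seen until 7.36 months. The same grid explains why the median does not move at f of 10% or below.

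**Other true medians.** The 6-month gaps at f = 10%, 20% and 30% are 2.6–3.3, 5.3–6.8 and 7.9–10.7 points for a median of 4 months, and 1.9–2.4, 3.8–5.0 and 5.9–7.8 points for 10 months.

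**Scale.** With n = 30 and 6-month PFS near 52%, the 95% CI half-width is about 1.96 × √(0.52 × 0.48 / 30) = 0.18, or 18 points, ignoring censoring.

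**Not computed.** DOR was not simulated, nor was new therapy as a censoring cause in its own right. For both, the argument rests on the mechanism alone.

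**The case against.** A reader might infer that scanning ends at discontinuation, so that progression after that point cannot be documented. The documents do not go that far. Protocol 8.2 says assessments are not required; it does not forbid them, and Appendix B asks for effort to document progression after treatment stops.

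Timing also matters. The SAP is based on Amendment 3 (SAP 2.1). The amendment log in Protocol Appendix C says the post-treatment disease follow-up text was removed in Amendment 4 (25 NOV 2020), and describes the change as applying after the primary efficacy analysis. By then, it says, every participant had at least 6 months of follow-up or had discontinued. Much of the PFS data may therefore have been collected while post-treatment scans were still expected, and the 6-month gaps above should not be put down to the current wording of 8.2 alone. This narrows the concern without removing it: the undocumented-progression and new-therapy rows censor under any amendment, and the SAP states that it carries forward to later ones.

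Deaths are counted as events and recover some of the loss. That recovery is partial. A death after two or more missed scans goes back to the last valid scan before the gap, and one after new therapy is also lost. The SAP does not say whether scans that are no longer required count as missed.

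PFS and DOR are secondary and descriptive, the Table 5 benchmarks are for ORR only, and at n = 30 the CI is wider than any bias shown. This limits the severity. The CI does not, however, allow for an error that runs in one direction. The planned listings let a reader find individual cases, but they give no alternative estimate.

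**Conclusion.** The point holds as a risk of upward bias in PFS and DOR from informative censoring, with no planned analysis to bound it. The direction is firm: 6- and 12-month PFS were higher under Table 4 in every scenario with any undocumented progression.

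The size is not known. For a true median of 6 months, 8-week scans and later deaths at most partly recovered, 6-month PFS would be overstated by roughly 2 to 3 points at a 10% share, 5 to 6 at 20% and 7 to 10 at 30%. The median may not change at 10% or below.

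A reader might take this as showing that PFS is materially overstated. The documents do not support that: they give no share of undocumented progression, and exposure is smaller to the extent that post-treatment scans were required before Amendment 4. The primary endpoint, ORR, does not use Table 4. This is a low-cost improvement to secondary estimates, not a flaw in the main result.

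**What to change.** Keep Table 4 as the main rule and make these changes:

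1. **Sensitivity analysis.** Prespecify one for PFS and DOR that counts as events: discontinuation or withdrawal for progression with no RECIST PD on record; start of new anticancer therapy; and PD or death after two or more missed scans. State whether scans that are no longer required count as missed.
2. **Reporting.** Give 6- and 12-month PFS beside the medians for both analyses, by cohort, since the median can hide the difference. Report the number of participants in each Table 4 row by cohort.
3. **Protocol text.** Reconcile Protocol 8.2 with Appendix B on imaging after discontinuation.

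The cost is one extra table per endpoint and no new imaging. The primary reason for discontinuation is already recorded (Protocol 7.1.2). It does not separate clinical from radiologic progression (7.1.1), but progression as the reason with no RECIST PD on record identifies the cases. Post-study therapy status is collected, though Table 3 schedules it only at end of treatment and the 28-day visit, so later starts may be missed.

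The downside is that counting every new therapy as an event can understate PFS. The two analyses should be read as bounds, not as a wrong and a right answer.

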7.3.3.3. Progression-Free Survival

Progression-free survival is defined as the time from the first dose of study drug to the date of the first PD according to RECIST v1.1 or death due to any cause. Progression-free survival will be analyzed by the Kaplan-Meier method, including estimated median with 95% CI and KaplanMeier estimated probabilities at several timepoints. If participants have no observed death or disease progression before data cutoff or new anticancer therapy, the participants will be treated as censored at their last adequate tumor assessment before data cutoff or new anticancer

therapy according to Table 4. Date of death will be determined using the Death Report, Survival Follow Up, and Subject Status eCRFs.

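### SAP Table 4 censors some observed deaths and progressions that the PFS text counts as events, and its rows overlap with no stated precedence

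*SAP*

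**What the plan says.** Protocol 10.4.2.3 defines PFS as time from first dose to first documented progression or death from any cause, and allows censoring on one condition: "If an event is not observed, PFS will be censored at the last adequate tumor assessment before cutoff or new anticancer therapy". SAP 7.3.3.3 has the same definition and refers to Table 4 for a restricted group: "If participants have no observed death or disease progression before data cutoff or new anticancer therapy".

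Table 4 (in SAP 7.3.3.1) has ten rows. Five matter here:

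- Row 1, "No baseline tumor assessments": censored at Day 1.
- Row 2, "No valid postbaseline response assessments in the absence of death prior to first scheduled tumor assessment": censored at Day 1.
- Row 8, "Death before first progressive response assessment": event at the date of death.
- Row 9, "Death between adequate response assessments": event at the date of death.
- Last row, "Death or documented progression immediately after missing 2 or more consecutive scheduled tumor assessment": censored at the last valid scan before the missed ones.

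For DOR, Protocol 10.4.2.1 and SAP 7.3.3.1 likewise censor only participants without progression or death, but the SAP does so "following the same algorithm as censoring of PFS (see Table 4").

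**The concern.** The text and the table give different answers for participants whose progression or death was observed. The text never sends such participants to a censoring rule, yet two parts of the table censor them.

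The table also disagrees with itself for deaths. Row 8 is unqualified, so it covers deaths that row 2 or the last row censors. Neither Table 4 nor the text of SAP 7.3.3.1 and 7.3.3.3 says which row prevails.

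Two programmers could follow this SAP faithfully and give the same participant opposite statuses on dates weeks apart. PFS would then not be fully reproducible from the plan. DOR inherits the missed-scan part of the problem.

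**Working it through.** **Step 1. Classify example participants.** None has earlier PD or new anticancer therapy. Scans are every 8 weeks (SAP 4.1.6, year 1).

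| Participant | PFS text | Table 4 |
|---|---|---|
| Baseline scan, no valid postbaseline scan, death at week 12 | Event, week 12 | Row 2: censored Day 1. Row 8: event, week 12 |
| SD at week 8, weeks 16 and 24 missed, death at week 26 | Event, week 26 | Row 8: event, week 26. Last row: censored week 8 |
| SD at week 8, weeks 16 and 24 missed, PD at week 32 | Event, week 32 | Last row: censored week 8 |

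Row 2 exempts only a death before the first scheduled scan, so week 12 is not exempt. Row 1 has no exemption for death, but should rarely apply because measurable disease (Protocol 5.1) and baseline imaging (Protocol 8.2.1) are mandatory. Row 7 (new anticancer therapy) agrees with the text.

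**Step 2. Figures in the plan.** The documents give no PFS rate, event count or missed-scan rate, so there is no PFS figure to reproduce. For scale only, the exact 95% intervals in Protocol Table 13 reproduce in all six rows; 12/30 gives 40.0% (22.7 to 59.4).

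**Step 3. Row 2 against row 8.** Let q be the affected fraction, S the six-month PFS in the others, and u the proportion of affected participants alive at month 6. Row 8 gives (1 - q)S + qu. Row 2 gives S, because Day-1 censoring adds no information. The shift is q(S - u). Assume S = 0.50 to 0.60 and n = 30.

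- One affected, u = 0: 29/30 x 0.50 = 48.3% becomes 50.0%, and 29/30 x 0.60 = 58.0% becomes 60.0%. The shift is +1.7 to +2.0 points.
- Two affected, u = 0: 2/30 x 0.50 to 2/30 x 0.60, or +3.3 to +4.0 points.
- One affected, later deaths (alive at week 8, then median survival 13 to 39 weeks): u = 0.5^(18/13) = 0.38 to 0.5^(18/39) = 0.73. The shift runs from (0.50 - 0.73)/30 = -0.8 to (0.60 - 0.38)/30 = +0.7 points.

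**Step 4. Worked case for the last row.** Take 30 participants, one of them the third row of the table above. The other 29 have 5, 5, 4, 3, 2 and 2 PDs at weeks 8, 16, 24, 32, 40 and 48, and 8 are censored at week 56.

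- Counted as an event: six months 16/30 = 53.3%; twelve months 8/30 = 26.7%.
- Censored at week 8, after that week's events: six months 25/30 x 19/24 x 15/19 = 52.1%; twelve months 25/30 x 8/24 = 27.8%.

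The estimate falls at one timepoint and rises at the other, so the direction is not fixed.

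**Step 5. Simulated range for the last row.** All inputs are assumptions. Shifts are last row minus all-events, in percentage points.

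| Scenario | Events censored | 6 months | 12 months |
|---|---|---|---|
| PD on drug, median 24, 32 or 40 weeks; 5-20% of scans missed independently | 0.6-8.8% of PDs | 0.0 to +0.3 | +0.1 to +1.8 |
| Same, but a 50% chance of missing the next scan after a miss | 6-22.5% of PDs | -1.9 to -0.2 | +0.3 to +3.4 |
| Deaths off drug: PD median 32 weeks; 10-30% stop drug without PD at weeks 8-52; death median 13-39 weeks later; off-drug scans count as scheduled | 36-74% of off-drug deaths | -1.2 to -0.1 | -1.3 to +0.2 (cutoff week 104) |
| Harsher: 5-20% of the cohort stop scans after week 8 or 16 and all die after at least two missed scans; PD median 16, 26 or 40 weeks | All such deaths | about -0.5 to -6 | about +0.4 to +8 |

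In the third scenario the share of deaths censored falls to 0% if off-drug scans do not count as scheduled. With cutoff at week 52 its twelve-month estimate is uninformative, because event-free participants on drug are all censored at week 48. In the harsher scenario the typical Kaplan-Meier median is unchanged for assumed medians of 16 and 26 weeks and moves from about 40 to 48 weeks for 40.

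**The case against.** The strongest reply is that Table 4 is plainly the operating algorithm. It contains event rows as well as censoring rows, so the PFS paragraph gives the general rule and the table the special cases. On that reading the specific last row qualifies the general row 8, and row 9, which covers deaths between adequate assessments, points the same way. Censoring after two missed scans is a recognised convention. Protocol 10.4 calls itself a summary and leaves missing-data procedures to the SAP.

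Much of this stands. The missed-scan rule is permissible, and the entry of no changes in SAP 10.1 is defensible. The override of row 8 by the last row is a fair inference, but it is not written, and SAP 7.3.3.3 still directs only event-free participants to the table. Applied to row 2, the same specific-over-general reading discards an observed death at Day 1.

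Three further points limit the finding:

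- The pure clash of rows 2 and 8 is narrow. Once two scans have been missed (about week 17 with the window), the last row also points to censoring. Under the later-death model in Step 3 only 1 - 0.5^(9/39) = 15% to 1 - 0.5^(9/13) = 38% of deaths fall before then.
- The two off-drug-death scenarios do not overlap at twelve months, so neither establishes a size.
- What was scheduled after drug stopped cannot be settled here. Current Protocol 8.2 requires no scans then, but the SAP rests on Amendment 3, whose schedule is not in the documents.

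The PFS and DOR listings in SAP Appendix A make individual classifications auditable, but they do not supply the rule.

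**Conclusion.** The concern holds. Table 4 censors observed deaths and progressions that the PFS text counts as events, rows 2 and 8 give opposite results for the same death, and no precedence is stated. Row 2 is wrong as written for a known death after the first scheduled scan. The last row is an acceptable rule that is stated inconsistently with the text. Confidence in the wording point is high.

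The size is uncertain because the documents give no rates. One or two affected participants, or the milder scenarios, shift PFS by at most about 4 points. Only the harsher scenario, at 20% of the cohort, reaches about 8. All of these are small beside the sampling error of a 30-participant cohort.

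The consequence is minor to moderate. PFS and DOR are descriptive secondary endpoints with no hypothesis test, and ORR and OS do not use these rules. The change should be made, but the primary result does not depend on it.

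**What to change.** 1. In rows 1 and 2, limit Day-1 censoring to participants not known to have died. A death without earlier PD or new anticancer therapy then falls to row 8, subject to item 2.
2. Make SAP 7.3.3.1, SAP 7.3.3.3 and Table 4 agree on one main rule.
   - *Option A:* all observed deaths and PDs are events, as the protocol text says, with the two-missed-scan rule as a sensitivity analysis.
   - *Option B:* the two-missed-scan rule is the main one. Write it into SAP 7.3.3.3 as an explicit exception that takes precedence over row 8, say how it applies when no postbaseline scan is valid, note it in SAP 10.1, and report the all-events version beside it.
3. Count a scan as missed only if the protocol version in force required it of that participant. Confirm the 8-weekly then 12-weekly schedule in SAP 4.1.6 against that version; the current Protocol Table 3 shows only the 8-weekly interval.

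The cost is SAP wording and one extra PFS and DOR run on existing data. Option B adds a second table and the SAP 10.1 note. No new scans or data are needed.
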